5 BASIC STUDY DESIGN

Vestibulodynia UPDATE is a multi-center, randomized, double-blind, placebo-controlled trial designed to determine the efficacy of peripheral lidocaine/estradiol cream, centrally-targeted nortriptyline pills, and combined treatments compared to matching placebo with the primary endpoints of change in pain, self-reported health, and cytokine/microRNA measures at 16 weeks and secondary endpoints of change in these measures at 8 weeks and 24 weeks.

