12 OUTCOME DETERMINATIONS

Aim 1. Determine the efficacy of peripheral, central, and combined treatments in alleviating pain among women with VBD-p and VBD-c.

Primary Endpoints:

- Ia. pain score during tampon test at 16 weeks
- Ib. self-reported pain *via* SF-MPQ at 16 weeks

Secondary Endpoints:

- Ila. experimental pain *via* local and remote PPTs at 16 weeks
- Ilb. COPC pain levels *via* COPC follow-up survey at 16 weeks
- Ilc. Pain scores and PPTs at 8 weeks and 24 weeks

Aim 2. Determine the efficacy of peripheral, central, and combined treatments in improving patient reported outcomes among women with VBD-p and VBD-c.

Primary Endpoints:

- Ia. self-reported physical/mental health *via* SF12v2 at 16 weeks
- Ib. sexual health *via* PROMIS at 16 weeks

Secondary Endpoints:

- Ila. mood *via* SCL-27 at 16 weeks
- Ilb. somatic awareness *via* PILL at 16 weeks
- Ilc. perceived stress *via* PSS at 16 weeks
- Ild. sleep *via* sleep scale at 16 weeks
- Ile. Patient reported outcomes at 8 weeks and 24 weeks

Aim 3. Determine the efficacy of peripheral, central, and combined treatments in normalizing cytokine and microRNA expression profiles in vaginal and blood tissues collected from women with VBD-p and VBD-c.

Primary Endpoints:

- Ia. cytokine levels *via* mesoscale discovery assays at 16 weeks
- Ib. microRNA levels *via* sequencing read at 16 weeks

Secondary Endpoints:

- Ila. cytokine and microRNA levels at 8 weeks and 24 weeks
- Ilb. Aim 3 will also identify cytokine and microRNA biomarkers at baseline that predict treatment response at 8, 16, and 24 weeks

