15.4 Analysis of the Aim 3 Endpoints

Cytokine Expression levels will be measured in vaginal lavage samples and plasma isolated from whole blood. We will use a standard Human MesoScale Discovery multiplex kit to measure 36 inflammatory mediators (4 tier-1 and 32 tier-2).

Tier-1 mediators include the pro-inflammatory cytokines IL-1 β ,⁵⁹⁻⁶¹ IL-8,^{7,60,62} and IL-17⁶³ and anti-inflammatory cytokine IL-1ra.^{7,61} These cytokines were selected based on previous associations with VBD case status and symptom severity.

Tier-2 mediators include cytokines (e.g., interleukin 6; IL-6), chemokines (e.g., monocyte chemoattractant protein 1; MCP1), and growth factors (e.g., vascular endothelial growth factor; VEGF) that are involved in peripheral and central sensitization, inflammation, and chronic pain.¹²⁸

miRNA Expression levels will be measured in vaginal swab samples and blood. We will isolate total RNA and then ship the RNA to UT Health Genome Sequencing Facility (GSF), directed by [name]. The GSF core will perform small RNA library preparation and sequencing.

Data Analysis. The two primary statistical questions for Aim 3 are: 3a) At baseline, is there an inverse association between VBD 'centralness' score (determined by the number of COPC sites) and the levels of Tier-1 cytokines in vaginal samples; and a positive association between VBD 'centralness' score and the levels of Tier-1 cytokines in plasma samples? 3b) Do biomarkers in vaginal fluid predict response to peripheral treatment and biomarkers in blood predict response to central treatment?

To answer question 3a, we will fit a linear regression model where cytokine level (skewed variables will be transformed (e.g., log, box-cox) to approximate normal distribution) will be a continuous dependent variable and VBD 'centralness' score, will be the main predictor of interest. Covariates will include age and race. Significance of regression coefficient associated with the 'centralness' score will be evaluated using an F-test and significance threshold (alpha) Bonferroni-corrected for the number of cytokines assessed (4 cytokines corresponding to 4 statistical tests). Subgroup means, mean differences and 95% confidence intervals will be output.

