To answer question 3b, we will fit a MMRM model analogous to 1a, with additional terms of treatment cytokine (in blood and vaginal samples) interaction, visit cytokine interaction, and treatment visit cytokine interaction. Significance of additional interaction terms will be evaluated using an F-test. Significant ($p < 0.05$) F-test will suggest that treatment effects by nortriptyline or lidocaine/estradiol cream or both, are modified by cytokines.

Secondary analyses for Aim 3 will include the association of Tier 2 biomarkers (cytokines and miRNAs) with VBD subtype and interaction with treatment response. These analyses will be analogous to those specified for questions 3a and 3b, with p-value thresholds kept at 0.05 due to exploratory nature of these analyses. In our secondary analyses we will also evaluate the change of biomarker concentrations (blood and vaginal samples) over time (at 0, 8, 16, and 24 weeks) in each treatment group and VBD subtype. We hypothesize that these biomarkers may serve as intermediate phenotypes for treatment success in VBD patient subgroups.

Expected Outcomes. 1) Women with VBD-p will have higher levels of inflammatory mediators in peripheral vaginal samples, while women with VBD-c will have higher levels of inflammatory mediators in circulating blood measured at the baseline visit (0 weeks). 2) Abnormalities in baseline vaginal cytokine and miRNA biomarkers will predict a positive response to peripheral lidocaine/estradiol treatment, while abnormalities in blood biomarkers will predict a positive response to centrally-targeted nortriptyline or combined treatment. 3) Peripheral treatment will resolve abnormalities in vaginal biomarkers evaluated at 8, 16, and 24 weeks, while central treatment will resolve abnormalities in blood biomarkers evaluated at 16 weeks.

All analyses will be performed using the Intent-to-Treat (ITT) population. The ITT population will include all randomized participants. Participants will be grouped according to their randomized allocation, regardless of whether the allocated therapy was administered or switched.

Any deviations from the statistical analyses described above, due to unforeseen circumstances, will be documented in the Statistical Analysis Plan (SAP).

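### Aim 3's primary endpoints, cytokine and microRNA levels at 16 weeks, have no specified between-arm test

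*Combined protocol and SAP*

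**What the plan says.** Section 12 (and the table in Section 2) states Aim 3 as an efficacy aim: "Determine the efficacy of peripheral, central, and combined treatments in normalizing cytokine and microRNA expression profiles". Its two primary endpoints are "Ia. cytokine levels *via* mesoscale discovery assays at 16 weeks" and "Ib. microRNA levels *via* sequencing read at 16 weeks". Section 5 gives the comparator; the treatments are "compared to matching placebo with the primary endpoints of change in pain, self-reported health, and cytokine/microRNA measures at 16 weeks".

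Section 15.4 then names two primary statistical questions for Aim 3:

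- **3a:** "At baseline, is there an inverse association between VBD 'centralness' score (determined by the number of COPC sites) and the levels of Tier-1 cytokines"? This direction applies to the vaginal samples; the opposite one is asked of plasma.
- **3b:** "Do biomarkers in vaginal fluid predict response to peripheral treatment and biomarkers in blood predict response to central treatment"?

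Secondary analyses follow. Tier-2 mediators and microRNAs are analysed by analogy with 3a and 3b, "with p-value thresholds kept at 0.05 due to exploratory nature of these analyses". After that comes one sentence on biomarkers as outcomes: "In our secondary analyses we will also evaluate the change of biomarker concentrations (blood and vaginal samples) over time", at the four visits, for each treatment group and subtype. The third expected outcome in Section 15.4 is that peripheral treatment resolves vaginal abnormalities and central treatment resolves blood abnormalities.

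**The concern.** An aim about the efficacy of treatment in normalising biomarkers needs the randomised comparison: biomarker level after treatment, active arm against placebo. Section 15.4 describes a change over time group by group instead. Such a change mixes the treatment effect with regression to the mean, time and assay drift, all of which can move the placebo arm too. Followed as written, the plan could support a claim that a treatment normalised a cytokine without a test of whether placebo did the same, although the trial has a randomised placebo arm.

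MicroRNA is in a weaker position still. It is co-primary in Section 12, yet apart from the change-over-time sentence it appears in Section 15.4 only among the Tier-2 analyses at an uncorrected 0.05. Those analyses concern association with subtype and interaction with treatment response, not the effect of treatment on microRNA.

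**Working it through.** **Step 1. What each specified analysis uses as outcome.**

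| Analysis (Section 15.4) | Status | Outcome | Biomarker's role | Arm-versus-placebo contrast on biomarker |
|---|---|---|---|---|
| 3a | primary | baseline Tier-1 cytokine | outcome at week 0 | none; no treatment term |
| 3b | primary | tampon-test pain (outcome of model 1a, Section 15.2) | effect modifier | none |
| Tier-2 and microRNA analogues of 3a and 3b | secondary | as in 3a and 3b | as in 3a and 3b | none |
| Change over time | secondary | biomarker at 0, 8, 16 and 24 weeks | outcome | none stated; no model, no alpha |

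Only the last row has a 16-week biomarker level as outcome. Calling it primary would not close the gap, because it still contains no contrast between arms. Section 15.2 shows how the plan writes such a contrast when it intends one: an overall F-test, then each of the three active arms minus placebo in least-squares means, at a Bonferroni threshold for three tests.

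**Step 2. The plan's only biomarker power figure.** Section 15.6 states power of 0.84 or more for a difference of 0.4 SD, with 192 VBD-c and 128 VBD-p women and alpha adjusted for four cytokines. I take this as two-sided 0.05/4 = 0.0125.

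- Noncentrality = 0.4 / √(1/128 + 1/192) = 3.505.
- Normal approximation: Φ(3.505 − 2.498) = 0.843.
- Exact noncentral t, 318 df: 0.839.

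The stated figure reproduces. It describes a baseline comparison of subtypes and says nothing about treatment.

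**Step 3. Power for the missing contrast.**

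Inputs:

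- 400 women with 20% attrition (Section 15.6) leave 400 × 0.8 = 320.
- Allocation 1:1:1:1 (Section 5.3) gives 320/4 = 80 per arm.
- The documents give no treatment effect on any biomarker, so 0.4 SD is borrowed from Step 2 as an assumption.

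Noncentrality = 0.4 / √(1/80 + 1/80) = 2.530, with 158 df. Exact two-sided power:

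| Alpha | Covers | Critical t | Power |
|---|---|---|---|
| 0.05 | one contrast | 1.975 | 0.71 |
| 0.05/8 = 0.00625 | 4 cytokines × 2 sample types | 2.772 | 0.41 |
| 0.05/24 = 0.00208 | 4 × 2 × 3 active arms | 3.130 | 0.28 |

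**Step 4. Effect of adjusting for baseline.** These figures take no credit for baseline adjustment. The documents give no correlation between visits for biomarkers. If the 0.5 that Section 15.6 assumes within subjects (for the pain score) also held here, the residual SD would shrink by √(1 − 0.5²) = 0.866. Noncentrality would rise to 2.530/0.866 = 2.921, and power to about 0.83, 0.56 and 0.42.

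**The case against.** The strongest reply is that the plan does not exclude a comparison of arms. Section 5 promises one against placebo, and evaluating change in each treatment group includes the placebo group, so its trajectory would be visible. This stands as far as it goes. A reader might infer that the biomarker effect will never be tested against placebo, and the documents do not support that. They support only that no model, contrast or alpha is specified. Viewing four trajectories side by side is not a test. Section 15.4 mentions a SAP only as the place to record deviations, so it cannot be presumed to supply one.

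Two other stronger readings also fail:

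- A reader might take the exploratory label and the 0.05 threshold to govern the change-over-time analysis. In the text they attach to the Tier-2 analogues of 3a and 3b. The change-over-time sentence comes later, is only secondary and has no threshold.
- A reader might count the false positives to expect across within-group tests. The plan specifies neither those tests nor an alpha for them. The figure of more than 750 microRNAs in Section 3.4 comes from an array platform in an earlier study, whereas this trial uses sequencing.

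It can also be said that the heading of Section 3.4 words Aim 3 as finding biomarkers that predict response, which 3b does address. That is true. The documents carry two versions of the aim, and the authors may choose between them, but Sections 2, 5 and 12 currently commit to the efficacy version.

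**Conclusion.** The point holds as a gap in specification: two declared primary efficacy endpoints have no specified efficacy test. It goes beyond labelling, because the one stated method, change within each group, cannot answer the aim's question whatever status it is given. The pain and patient-reported analyses are unaffected.

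The gap itself follows from the text and rests on no numerical assumption. The power figures do. They assume 80 evaluable women per arm, a 0.4 SD effect that the documents do not claim for treatment, and two-sided tests. Under those assumptions power for one arm against placebo runs from 0.71 at 0.05 to 0.28 at 0.05/24, or from 0.83 to 0.42 if the baseline correlation were 0.5.

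**What to change.** Choose one of two routes and make Sections 2, 5, 12 and 15.4 agree.

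**Route 1: specify the test.**

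- For each Tier-1 cytokine and sample type, fit a model analogous to 1a. The outcome is the transformed biomarker at the post-baseline visits and its baseline value is a covariate. Week 0 should not also be in the outcome vector.
- Test treatment at 16 weeks with an overall F-test, then active-minus-placebo contrasts.
- Control multiplicity over 4 cytokines × 2 sample types and the 3 arm contrasts. With plain Bonferroni that is 24 contrasts; correcting for the 8 cytokine-by-sample combinations alone would leave out the arms.
- Add the subtype interaction as in model 1b, since the aim concerns both subtypes.
- Use the same contrasts with false-discovery-rate control for microRNAs and Tier-2 mediators.
- Report within-arm change as description only, and add a power statement for the treatment contrasts.

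**Route 2: reclassify.** Make the 16-week biomarker endpoints secondary or exploratory and drop the efficacy wording for Aim 3.

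Appendix A already schedules blood and vaginal samples at baseline, 8, 16 and 24 weeks, so Route 1 needs no new data collection, only text and model fits. Its real cost is modest power for the corrected contrasts, which the plan should state openly. Route 2 costs the efficacy claim.

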Women with VBD display signs of mucosal inflammation¹¹ accompanied by enhanced production of the pro-inflammatory cytokines interleukin 1 β (IL-1 β),⁵⁹⁻⁶¹ interleukin 8 (IL-8),^{60, 62} and interleukin 17 (IL-17)⁶³ in the vaginal vestibule and/or in circulating blood. A study by Gerber et al. further demonstrated that increased levels of IL-1 β were accompanied by reduced levels of interleukin 1 receptor antagonist (IL-1ra),⁶¹ an anti-inflammatory cytokine that negatively regulates the expression of IL-1 β and IL-8.⁶⁴⁻⁶⁶ To determine inflammatory profiles in VBD-p and VBD-c subtypes, we used a multiplex assay to measure circulating cytokines in blood.⁷ Compared to HC, women with VBD-p had increased levels of both IL-8 and IL-1ra (Figure 3). In contrast, women with VBD-c had increased levels of IL-8 with no increase in IL-1ra, indicating a pro-/anti-inflammatory imbalance. There have been no studies of these changes in vaginal tissues. We performed a pilot study to demonstrate our ability to measure cytokine protein in vaginal lavage samples.

Results
show that IL-8 is detectable by multiplex in 7 HC vaginal lavage samples (Figure 3). These results establish the utility of cytokines as diagnostic biomarkers for functional VBD-p and VBD-c groups.

[figure not shown]

Figure 3. VBD-p and VBD-c exhibit different cytokine profiles. Data are Mean \pm SEM. * p <0.05, ** p <0.01 vs HC.

[figure not shown]

Figure 3. IL-8 is detectable in VL samples. Data are Mean \pm SEM.

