7 STUDY POPULATION AND ELIGIBILITY CRITERIA

7.1 Study Population

The study population is women with VBD aged 18-50 of any race or ethnicity. Based on historical patterns of recruitment, we expect the racial distribution will be 65% White, 10% Asian, 10% Hispanic, 8% African-American, and 6.5% other groups. This distribution is quite similar to that among people reporting VBD in other U.S. demographic populations.

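### Aim 3 claims that treatment normalises biomarkers, but the plan defines no normal level and never tests a biomarker against placebo

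*Combined protocol and SAP*

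**What the plan says.** Section 12 (and, in similar words, Sections 2 and 4) makes the third aim the efficacy of the treatments in "normalizing cytokine and microRNA expression profiles in vaginal and blood tissues collected from women with VBD-p and VBD-c". Its first primary endpoint is simply "cytokine levels *via* mesoscale discovery assays at 16 weeks"; microRNA level at the same visit is the second. Section 5 describes the trial as comparing the treatments with matching placebo and counts these biomarker measures among the primary endpoints.

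Section 15.4 names two primary questions. Question 3a is a baseline association between Tier-1 cytokines and the COPC count. Question 3b asks whether biomarkers predict the response to treatment. Biomarker change under treatment comes only under secondary analyses, which will "evaluate the change of biomarker concentrations (blood and vaginal samples) over time (at 0, 8, 16, and 24 weeks) in each treatment group" and by VBD subtype. The expected outcome is that "Peripheral treatment will resolve abnormalities in vaginal biomarkers evaluated at 8, 16, and 24 weeks, while central treatment will resolve abnormalities in blood biomarkers".

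On who is sampled, Section 7.1 says: "The study population is women with VBD aged 18-50 of any race or ethnicity". Section 5.1 adds about five feasibility volunteers per site, who are exempt from the eligibility criteria and serve to standardise procedures. Healthy controls appear only in the background: 22 women in the earlier cohort (Section 3.2) and 7 vaginal lavage samples used to show that IL-8 can be detected (Section 3.4).

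**The concern.** To say that a level was normalised, or that an abnormality resolved, one must know what normal is and in which direction abnormality lies. The plan supplies neither as part of an analysis. It also has no comparison that would attribute a biomarker change to treatment: movement within an arm mixes the treatment effect with time and with whatever happens on placebo.

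At stake is the headline conclusion of one of the three aims. A reader of the final report could be told that the cream or the pill restored a normal inflammatory profile, when the analysis had shown only that some concentrations changed between visits. A placebo contrast alone would not cure this. It would show that treatment moved the marker, still not that the marker became normal.

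**Working it through.** The plan gives no figure for normalisation, so the check is mainly of text, with three short calculations.

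**1. What each Section 15.4 analysis can answer**

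| Analysis | Outcome | Role of biomarker | Placebo contrast on biomarker | Healthy reference |
|---|---|---|---|---|
| 3a (primary) | Baseline Tier-1 level | Outcome, before treatment | None | None |
| 3b (primary) | Pain score, model as in 1a | Effect modifier | None | None |
| Tier-2 and miRNA (secondary) | As 3a and 3b | As 3a and 3b | None | None |
| Change over visits (secondary) | Biomarker concentration | Outcome | None; within arm and subtype | None |

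The primary endpoints, levels at week 16, are therefore not the outcome of either primary question.

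**2. The plan's own Aim 3 figure**

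Section 15.6 gives power of 0.84 for question 3a: 128 VBD-p against 192 VBD-c, 0.4 SD, alpha 0.05/4 = 0.0125 two-sided.

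- Standard error in SD units: √(1/128 + 1/192) = 0.114.
- Power: Φ(0.4/0.114 − 2.498) = Φ(1.008) = 0.843 (noncentral t: 0.839).

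The figure reproduces. It concerns a baseline difference between two patient groups and says nothing about return to a healthy level.

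**3. Could the earlier healthy controls serve as the reference?**

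- Implied SDs from Section 15.6: IL-8, 2/0.4 = 5 pg/mL; IL-1ra, 240/0.4 = 600 pg/mL.
- Patient-control gaps given there: IL-8, 4/5 = 0.8 SD; IL-1ra, 300/600 = 0.5 SD.
- 95% half-width of a healthy mean from 22 women: t(0.975; 21)/√22 = 2.080/4.690 = 0.44 SD. From 7 women it is 0.92 SD.

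This assumes that all 22 gave cytokine data and that their SD equals the implied one. The uncertainty in normal is then almost as large as the IL-1ra gap and more than half of the IL-8 gap. The earlier cohort's cytokines were measured in blood. Its miRNAs came from OpenArray cards, whereas the trial uses sequencing.

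**4. Direction of benefit**

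- IL-1β, IL-8, IL-17: Section 3.4 cites raised production in VBD and Section 15.4 labels them pro-inflammatory, so a fall is the implied benefit.
- Blood miRNAs: Table 3 gives directions against healthy controls for 6 + 7 + 4 = 17.
- IL-1ra: Section 3.4 reports "Compared to HC, women with VBD-p had increased levels of both IL-8 and IL-1ra", no rise in VBD-c (described as an imbalance), and a reduction in a cited study. Sections 2 and 3.1 call the VBD-p profile balanced and treat the missing rise in VBD-c as a lack of compensation. Question 3a nevertheless predicts that plasma Tier-1 levels, IL-1ra included, rise with centralness; the team's own blood data show the IL-1ra rise at the other end, in VBD-p.
- Individual Tier-2 mediators and vaginal miRNAs: no beneficial direction is stated.

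None of these directions is carried into an endpoint or a test.

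**5. What a week-16 placebo contrast could detect**

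Completers per arm: 320/4 = 80. The detectable difference at 80% power is (z for two-sided alpha + 0.842) × √(2/80) SD, unadjusted for baseline. Four cytokines, two sample types and three active arms make 4 × 2 × 3 = 24 contrasts.

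| Two-sided alpha | SD | IL-8 (×5 pg/mL) | IL-1ra (×600 pg/mL) |
|---|---|---|---|
| 0.05 | 0.443 | 2.2 | 266 |
| 0.0125 | 0.528 | 2.6 | 317 |
| 0.05/24 = 0.0021 (z = 3.078) | 0.62 | 3.1 | 372 |

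The contrast is workable for IL-8, whose gap is 4 pg/mL, and marginal for a change of the size of the IL-1ra gap of 300 pg/mL. These values assume blood SDs; the documents give none for vaginal fluid.

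**The case against.** The best defence is that the operative text is neutral. The endpoints are levels, the secondary analysis is of change, model 3b uses no abnormality cut-off, and no success rule for normalisation exists. The disputed wording sits in the aim and the expected outcomes, and the Tier-2 work is labelled exploratory. That is accurate, but it supports rewording: the aim claims something that no listed analysis can deliver.

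The defence also blocks several stronger readings that a reader might infer.

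- *Any movement, up or down, could be reported as success.* The documents do not support this for IL-1β, IL-8 and IL-17, where a rise could hardly be presented as benefit, nor for the blood miRNAs in Table 3.
- *A fall in IL-1ra would count as normalising in VBD-p.* The documents do not treat the raised level there as an abnormality to be reversed; they call it balanced. What stands is that no consistent direction can be read off for this marker.
- *Nothing is known about cytokines in vaginal tissue.* The sentence "There have been no studies of these changes in vaginal tissues" follows the subtype-specific blood findings and most naturally refers to those. The same section cites raised cytokines in the vestibule and/or blood in VBD generally.
- *Only two of the 72 marker-by-sample series (36 × 2) have a healthy comparison.* That count would leave out the cited IL-1β and IL-17 findings, and the figure with the cohort's profiles is not available here.

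It can also be said that a placebo contrast is more than a change of wording. That is right, and the cost below includes it.

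**Conclusion.** The concern holds in a bounded form. The Aim 3 treatment claim has no defined normal level, no healthy reference in any analysis and no biomarker comparison with placebo. Followed as written, the plan supports a statement that markers changed within groups and nothing beyond it. Direction is implied for three of four Tier-1 cytokines and for 17 blood miRNAs but used nowhere. It conflicts for IL-1ra and is missing for individual Tier-2 mediators and vaginal miRNAs.

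The conclusion rests on the text, not on a disputed number, and the plan's stated power is arithmetically correct. The figure of ±0.44 SD depends on the two assumptions given with it; it shows only that borrowing the 22 earlier controls would not repair the gap. The point does not reach Aims 1 and 2, and it does not imply that the biomarker data are without value.

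**What to change.** 1. In Sections 2, 4, 12 and 15.4, restate the Aim 3 treatment objective as the week-16 biomarker level in each active arm compared with placebo. This matches the placebo comparison that Section 5 already announces.
2. In Section 15.4, add that contrast for the four Tier-1 cytokines in each sample type, using the same type of MMRM as for Aim 1 with the biomarker as outcome. Apply the transformation rule already given for 3a, and state the significance threshold for the resulting 24 contrasts.
3. State the expected direction for IL-1β, IL-8 and IL-17. Treat IL-1ra, the Tier-2 mediators and the vaginal miRNAs as two-sided with no claimed direction of benefit. Reconcile the 3a prediction for plasma IL-1ra with the background data.
4. State that no claim of normalisation will be made without a healthy reference measured on the same assay.

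No new participants, samples or assays are needed. The price is a more modest Aim 3 claim and a small amount of additional analysis.
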